Cryopreservation of frozen-thawed embryos has become an indispensable procedure in reproductive medicine. Mainly, thanks to the development of the vitrification procedure and the improvement of embryo survival rates after thawing (*Rienzi et al., 2017; Loutradi et al. 2008*), pregnancy rates have substantially increased. Likewise, the implementation of a single embryo transfer policy to reduce multiple pregnancies without lowering cumulative delivery rates (*Peeraer et al., 2014*) has led to an increase in surplus embryos deriving from an ovarian stimulation cycle. Besides, freeze-all strategies have been adopted for an increasing number of indications, namely to avoid ovarian hyperstimulation syndrome (=OHSS), or for preimplantation genetic testing (=PGT) patients, or in case of late follicular progesterone (P) rise or in case of endometrium- embryo asynchrony (*Bosch et al., 2016; Roque et al., 2015; Healy et al., 2016; Devroey et al., 2011; Shapiro et al., 2008; Racca et al., 2018; Groenewoud et al., 2017*). These developments have led to an increase in the number of frozen-warmed embryo transfer (FET) cycles performed in fertility centres over the last decade.

Despite this growing importance, little is known about the optimal endometrium preparation protocol prior to embryo transfer (*Ghobara et al., 2017; Groenewoud et al., 2017*). The two most common used treatment regimens to prepare the endometrium for embryo transfer are the so called natural cycle (NC) and the hormone replacement therapy (HRT) cycle. In a natural cycle the endometrium undergoes structural changes caused by consecutive exposure to estrogens and progesterone derived from the growing follicle. The moment of embryo transfer is determined by the occurrence of the natural ovulation, meaning on the fourth day after luteinizing hormone (LH) surge for cleavage stage embryos and for blastocysts on the sixth day (*Mackens et al., 2017*). HRT protocols are using exogenous administration of estrogens and progesterone in order to mimic a natural cycle and therefore endometrial development. The advantages of this latter protocol are the easy scheduling and minimal cycle monitoring. So far, no RCTs have been performed comparing a true NC (without hCG administration) and an HRT cycle for FET. However, concerns are raising about the high miscarriage rates reported in HRT cycles (*Tomás et al., 2012; Hreinsson et al., 2016; van de Vijver et al., 2016; van de Vijver et al., 2017*).

[figure not shown]
2. Study Flowchart and Design

Group A: NC (awaiting spontaneous LH surge)

Group B: HRT¹

¹ Progesterone supplementation is started when the endometrium is considered adequate after E2 administration. E2 supplementation vary between 1 to 3 weeks depending on the adequate proliferation of the endometrium.

Legend: B: serum hormone analysis (estradiol (E2), P, LH, follicle stimulation hormone (FSH));
US: ultrasound scan; P: progesterone

3. Study objectives and endpoints

The aim of the current RCT is to compare miscarriage rates (before 8 weeks) between true NC (awaiting spontaneous LH surge) and HRT FET cycles in PGT patients, with biopsy on day 5 of embryonic development. The advantage of performing the study in PGT patients is the exclusion of aneuploidy as a cause of miscarriage.

3.1 Primary outcome:

Miscarriage rate before 8 weeks of gestation, defined as a spontaneous loss of a clinical pregnancy before 8 weeks of gestational age, in which the embryo(s) is/are nonviable and is/are (not) spontaneously absorbed or expelled from the uterus (Zegers-Hochschild et al 2017).

3.2 Secondary outcomes:

Miscarriage rate after 8 weeks of gestation, defined as a spontaneous loss of a clinical pregnancy after 8 weeks but before 22 completed weeks of gestational age, in which the embryo(s) or fetus(es) is/are nonviable and is/are not spontaneously absorbed or expelled from the uterus (Zegers-Hochschild et al 2017).

Clinical pregnancy defined as a pregnancy diagnosed by ultrasonographic visualization of one or more gestational sacs or definitive clinical signs of pregnancy. In addition to intra-uterine pregnancy, it includes a clinically documented ectopic pregnancy (Zegers-Hochschild et al 2017).

Ongoing pregnancy rate defined as the number of pregnancies after 20 weeks of gestation.

4. Methodology

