4.5 Interventions

- Natural cycle FET (Group A)

Patients are asked to perform a blood sample, with evaluation of serum estradiol (E2), progesterone (P), luteinizing hormone (LH) and follicle stimulating hormone (FSH), on the first or second day of the menstrual cycle (day 1 is considered as the first day of fresh red blood loss before 12AM). If these serum hormonal values are considered basal for the beginning of the follicular phase, patients are asked to come back on day 10 to 12 of the cycle for blood sample and transvaginal ultrasound scan

in order to assess follicular growth. Depending on the values on day 1 or 2, the physician performing the daily monitoring can decide to perform an earlier examination if necessary.

The timing of ovulation is determined based on a combination of ultrasonography features (the presence of a dominant follicle and adequate endometrium) and endocrine hormonal values in serum blood samples. Ovulation is generally defined as an, at least, 180% increase of LH compared to the mean level in the previous 24h (Frydman et al., 1982).

Frozen-warmed embryo transfer will take place six days following the spontaneous LH surge. Another blood sample will be performed 12 days after embryo transfer measuring human chorionic gonadotrophin (hCG), progesterone and estradiol in order to assess the outcome of the FET cycle.

- Hormonal replacement therapy cycle FET (Group B)

Patients are asked to perform a blood sample, with evaluation of serum estradiol (E2), progesterone (P), luteinizing hormone (LH) and follicle stimulating hormone (FSH) on the first or second day of the menstrual cycle (day 1 is considered as the first day of fresh red blood loss before 12AM). If these values are considered basal for the beginning of the follicular phase, estrogen supplementation (Estradiol valerate, Progynova® 3x2mg/day) is started to induce proliferation of the endometrium. Blood sample and transvaginal ultrasound are thereafter performed ten to fourteen days later. If the endometrium is considered adequate (generally considered if triple line and above 6,5 mm thickness)(Liu et al., 2018), embryo transfer is scheduled on the sixth day of progesterone (vaginal micronized progesterone, Utrogestan® 2x200mg twice a day) supplementation.

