If the endometrium remains inadequate on day 10-14, estrogen priming will be prolonged with a maximum of 14 days of additional estrogen supplementation. If hereafter the endometrium stays below 6,5mm the cycle will be cancelled.

Another blood sample will be performed 12 days after embryo transfer measuring hCG, P and E2 in order to assess the outcome of the FET cycle.

In case of a positive pregnancy test, estrogen and progesterone supplementation will be continued until 8 weeks of gestation (in line with the onset of the luteo-placental shift) (Scott et al., 1991).

In case of escape spontaneous ovulation embryo transfer will be performed considering the presumable time of ovulation.

5. Treatment

- Group A: NC FET

In this group, no medication will be administered to the patients. The aim of this protocol is to detect the occurrence of a spontaneous LH surge in order to calculate the day of embryo transfer.

- Group B: HRT FRET

Estradiol valerate (Progynova[®], Bayer-Schering Pharma AG, Berlin, Germany) will be started on the first or second day of the menstrual cycle, in case of basal hormonal conditions, at a regimen of 2mg thrice a day. After ten to fourteen days of estrogen supplementation a check-up is planned with a blood sample and transvaginal ultrasound. If the endometrium is adequate (as above mentioned) transfer of the frozen-thawed embryo is planned on the sixth day of progesterone supplementation. We will use micronized progesterone vaginally (Utrogestan[®], Besins International) two capsules of 200 mg twice a day.

HRT cycles, using a consecutive administration of estrogen and progesterone, are used worldwide especially due to the advantage of easy and flexible scheduling and minimal monitoring which reduces the visits to the hospital compared to NC FRET. Although the universal use of HRT protocols in fertility centres no consensus is yet established concerning the ideal duration, route of administration or type of drugs used in order to prepare the endometrium for embryo transfer (Glujovsky et al., 2010).

We will adopt the above-mentioned protocol which is in line with the local protocol applied in the Centre of Reproductive Medicine in Brussels.

6. Data collection and Management

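### Does the flowchart footnote's range of 1 to 3 weeks of estradiol conflict with the longer priming allowed in section 4.5?

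*Protocol*

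**What the plan says.** Three places in the protocol bear on how long estradiol is given before progesterone in group B.

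- **Section 2, flowchart footnote.** "Progesterone supplementation is started when the endometrium is considered adequate after E2 administration". The next sentence reads "E2 supplementation vary between 1 to 3 weeks depending on the adequate proliferation of the endometrium".
- **Section 4.5, Interventions, group B.** Once estradiol has started, "Blood sample and transvaginal ultrasound are thereafter performed ten to fourteen days later". If the lining is not adequate at that point, "If the endometrium remains inadequate on day 10-14, estrogen priming will be prolonged with a maximum of 14 days of additional estrogen supplementation". The last step is "If hereafter the endometrium stays below 6,5mm the cycle will be cancelled".
- **Section 5, Treatment, group B.** Estradiol "will be started on the first or second day of the menstrual cycle, in case of basal hormonal conditions". The timing of the first check is repeated: "After ten to fourteen days of estrogen supplementation a check-up is planned with a blood sample and transvaginal ultrasound". This section says nothing about prolongation or cancellation.

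The word maximum appears only in section 4.5, where it applies to the additional days and not to the total.

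**The concern.** Estradiol priming is part of the definition of one of the two randomised interventions. A range of 1 to 3 weeks reads naturally as ending at 21 days, yet the section that describes the intervention lets priming run past that. Someone working from the flowchart and someone working from section 4.5 could disagree on whether priming on days 22 to 28 follows the regimen.

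If staff treated day 21 as an end point, some cycles would stop before transfer that section 4.5 would continue. A woman without a transfer in that cycle cannot have a miscarriage from it, so the two practices could in principle give slightly different event counts in the hormone replacement arm. That makes it worth checking whether the footnote really competes with section 4.5 as an instruction.

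**Working it through.** **Inputs**

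- Footnote range (section 2): 1 to 3 weeks, so 1 × 7 = 7 to 3 × 7 = 21 days.
- First check (sections 4.5 and 5): day *d* of estradiol, with *d* from 10 to 14.
- Longest prolongation (section 4.5): 14 days.
- Start of estradiol (section 5): cycle day 1 or 2.

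**Which period the footnote means.** It cannot be total exposure to estradiol, because section 4.5 continues estrogen to 8 weeks of gestation after a positive test. The preceding footnote sentence ties it to the phase before progesterone, which is the phase that section 4.5 schedules.

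**Longest priming under section 4.5**

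Longest priming = *d* + 14. Excess over the footnote = *d* + 14 − 21. Prolongation that satisfies both texts = 21 − *d*.

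| First check (day) | Longest priming (days) | Excess over 21 (days) | Prolongation within both texts (days) |
|---|---|---|---|
| 10 | 24 | 3 | 11 |
| 11 | 25 | 4 | 10 |
| 12 | 26 | 5 | 9 |
| 13 | 27 | 6 | 8 |
| 14 | 28 | 7 | 7 |

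The footnote's upper end cannot be reproduced from section 4.5 for any permitted check day.

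**Alternative reading.** Section 4.5 could mean cycle days when it speaks of an inadequate lining on day 10-14. The check then falls after 10 − 2 = 8 to 14 − 1 = 13 days of estradiol. Adding 14 gives 22 to 27 days, an excess of 1 to 6 days. The mismatch shrinks but remains.

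**Lower end.** A first check at 10 to 14 days lies inside 7 to 21 days, so there is no contradiction. However, no check in group B is scheduled as early as day 7, so the lower bound does not come from the schedule either. Both ends look like rounding to whole weeks.

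**Who is affected.** Only a woman whose lining is inadequate at the first check and who then needs more than 11 extra days (day-10 check), falling to more than 7 (day-14 check). The protocol gives no count of such women, so no effect on the primary outcome can be calculated.

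**What depends on the footnote**

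- Primary and secondary outcomes (sections 3.1 and 3.2): defined by pregnancy status and gestational age.
- Regression model (section 5.1): treatment arm, age, BMI, indication of infertility, embryo quality and outcome of the previous fresh attempt. Duration of estradiol is not included.
- Sample size (section 5.2): 9.9% against 18.4%, 80% power, 5% level. None of these is a duration.
- Deviation rule or per-protocol set based on priming time: none in the protocol.

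**The case for a change.** The best case for acting is that the footnote is more than loose description. It gives a bounded range with no softening word, whereas section 4.5 says generally when it means an approximation, as it does for ovulation and for an adequate lining. The footnote also makes duration depend on endometrial proliferation, the same condition that triggers the prolongation, so it ought to cover prolonged cases and does not. Duration of treatment belongs in a protocol and cannot be left to an analysis plan. The correction would take one line.

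Most of this stands as a criticism of the drafting. The two texts give different upper ends, and no reading brings section 4.5 down to 21 days. What does not stand is the step from there to two competing rules. The footnote never presents 3 weeks as a limit and says nothing about what happens on day 21. A reader who stops there has no instruction to follow, and section 4.5 supplies one for each step: the first check, the criterion for adequacy, the prolongation, its cap and the cancellation. The share of the prolongation lying beyond 3 weeks (3/14 = 21% to 7/14 = 50%) restates the same subtraction and does not show how often it happens.

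**Conclusion.** The mismatch is confirmed. The footnote ends at 21 days, while section 4.5 allows 24 to 28 days (22 to 27 on the cycle-day reading). It is a clerical slip between a summary footnote and a complete description of the intervention. Correcting it would change no outcome, estimate, test or sample size in the protocol, so the statistical plan stays as it is. Sections 2 and 4.5 should be brought into line in wording when the document is next edited. Which duration to state is for the clinical team, and nothing here favours either.

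This rests on two assumptions. First, staff follow the step-by-step text in section 4.5 and do not read an unstated stopping rule into the footnote. Second, no separate analysis plan defines adherence by days of estradiol. If one did, the two texts would have to agree before that set was fixed. The flowchart diagram itself was not legible in the copy used, so the reading rests on the footnote's words.

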4.2 Selection of study population

The study population consists of all PGT patients who fulfil the following inclusion criteria:

- Age between 18 and 42 years
- BMI under 35 kg/m²
- Regular menstrual cycle pattern (i.e. 24-35 days cycle)
- First, second and third ICSI-PGT cycle
- First frozen embryo transfer cycle following a fresh ICSI-PGT attempt
- PGT with trophectoderm biopsy on day 5 of embryonic development
- Signed informed consent

The exclusion criteria involve:

- Oligo-amenorrhea
- Age above 43 years
- BMI above 35
- Contraindications for the use of hormonal replacement therapy

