4.3 Screening

On the first consultation, the treating physician will inform the eligible PGT patients about the study. Patients willing to participate and fulfilling the inclusion criteria will be randomized to one of the two treatment arms following the fresh ICSI cycle if non-affected embryos are available. Informed consent forms will be signed either on the first day of the following menstrual cycle or on the moment of frozen-warmed embryo transfer.

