5.1 Statistical analysis

Continuous variables will be analyzed using the independent *t*-test or Mann–Whitney *U*-test depending on the normality of the distribution. Normality will be examined by the use of the Shapiro–Wilk test. Categorical variables will be analyzed by Pearson's chi-squared test or Fisher's exact test, as appropriate. To identify characteristics that may be related with the miscarriage rate, multivariate logistic regression analysis will be performed with the miscarriage rate as the dependent variable and transfer policy (NC versus HRT) as the main independent variable. Candidate variables considered for the analysis are: age, BMI, indication of infertility, percentage of patients with at least one top quality embryo and outcome of the previous fresh attempt. All candidate variables will be simultaneously entered into the logistic regression model. All tests will be two-sided with a level of significance set at $p < 0.05$. Analyses will be performed using STATA 15.0.

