5.2 Sample size calculation

Sample size calculation was performed using internal data of our centre considering early miscarriage rates (defined as miscarriage before 8 weeks of gestation). We observed in our PGT population in 2017 an early miscarriage rate per started FET cycle of 9,9% in the natural cycle group compared to 18,4% in the group using HRT.

Based on these results, 522 patients are required (261 in each treatment arm) to have an 80% chance of detecting, as significant at the 5% level, an increase in the primary outcome measure (early pregnancy loss) from 9,9% in the NC group to 18,4% in the HRT group.

7. Ethical consideration

The protocol will be submitted to the local Ethics Committee of UZ Brussel. Strict confidentiality of all personal and research data will be ensured. The recruiting centre will be required to sign a clinical trial agreement document detailing their commitment towards complying with the relevant laws, regulations, codes of practice and obligations to publication. There are no conflicts of interest.

No specific reimbursement will be given to patients participating in the study.

8. References

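### Does the trial need changing because its written criteria do not secure the claim that PGT patients have no aneuploid miscarriages?

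*Protocol*

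**What the plan says.** The aim in Protocol section 3 is to compare miscarriage before 8 weeks between natural and HRT cycles in women having PGT with a day-5 biopsy. One sentence of rationale follows: "The advantage of performing the study in PGT patients is the exclusion of aneuploidy as a cause of miscarriage". It carries no qualification, and aneuploidy is mentioned nowhere else in the protocol.

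The text bearing on which women and embryos enter is as follows.

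- The background expands the abbreviation only in general terms, as "preimplantation genetic testing (=PGT) patients".
- Section 4.2 opens with "The study population consists of all PGT patients who fulfil the following inclusion criteria". Its PGT items are "First, second and third ICSI-PGT cycle", a requirement that this be the first frozen transfer after the fresh attempt, and "PGT with trophectoderm biopsy on day 5 of embryonic development".
- Section 4.3 allows randomisation after the fresh cycle "if non-affected embryos are available". The term is not defined.
- Section 4.4 refers back to eligibility. Sections 4.5 and 5 (Treatment) deal with monitoring, timing and medication, and set no ploidy condition on the embryo.
- Section 5.1 lists age, BMI and indication of infertility as candidate variables, followed by "percentage of patients with at least one top quality embryo and outcome of the previous fresh attempt". Ploidy and type of PGT are not listed.
- Section 5.2 takes its planning rates from the centre's own records: "We observed in our PGT population in 2017 an early miscarriage rate per started FET cycle of 9,9" per cent with natural cycles, against 18.4% with HRT.

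**The concern.** A reader who sets the rationale beside the criteria sees a gap. As written, a woman whose embryo was tested for something other than chromosome number, and was called non-affected, would meet every criterion. The protocol would then contain aneuploid losses that section 3 says are excluded.

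Three things could be at stake:

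1. **Validity.** Aneuploid losses might distort the comparison of the arms.
2. **Power.** Losses unrelated to endometrial preparation add noise and could make 522 women too few.
3. **Interpretation.** A report could lean on section 3 to say that chromosomal error played no part in the observed miscarriages, without data to support it.

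Eligibility and the condition for randomisation belong in a protocol, so the mismatch cannot simply be left to an unseen SAP.

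**Working it through.** **Step 1: is the statement contradicted, or only not secured?**

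| Place | What it fixes | What it leaves open |
|---|---|---|
| Section 3 | Aneuploidy is excluded by studying PGT patients | How |
| Section 4.1 | One centre | – |
| Section 4.2 | Biopsy type and day, cycle rank | What the biopsy is tested for |
| Section 4.3 | Non-affected embryos must be available before randomisation | What non-affected covers |

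No section says that the centre's PGT omits chromosome number or that untested embryos will be transferred. Read together, sections 3 and 4.3 allow non-affected to include not aneuploid. They also allow the opposite. The documents therefore show an undefined term, not a false statement.

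**Step 2: does the planned sample size stand?**

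Inputs from sections 5.1 and 5.2: p₁ = 0.099, p₂ = 0.184, two-sided α = 0.05, power 80%. Allocation is 1:1 (section 4.1).

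Unpooled two-proportion formula:

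n = (z₀.₉₇₅ + z₀.₈₀)² × [p₁(1 − p₁) + p₂(1 − p₂)] / (p₂ − p₁)²

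= 7.849 × (0.0892 + 0.1501) / 0.085²

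= 7.849 × 0.2393 / 0.007225 = 260.01, rounded up to 261 per arm, or 522 in total.

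This is the protocol's figure. The pooled-variance version gives 263 per arm (526 in total), and its power at 261 per arm is 79.7%.

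**Step 3: could aneuploid losses make 522 too small?**

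Only if the planning rates were free of such losses and the trial were not. As an illustration under that assumption, add an equal number of percentage points to both arms:

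| Added to each arm | Rates | Power at 261 per arm | Pooled N |
|---|---|---|---|
| 2 points | 11.9% vs 20.4% | about 75% | 588 |
| 4 points | 13.9% vs 22.4% | about 71% | 644 |
| 6 points | 15.9% vs 24.4% | about 68% | 698 |

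Section 5.2 does not support that assumption. Its rates come from the centre's 2017 PGT population, with no restriction to euploid embryos stated. If the enrolled women resemble that population, whatever aneuploid losses occur are already in 9.9% and 18.4%, and nothing is to be added.

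**Step 4: would a supportive analysis in euploid-tested women be worth adding?**

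Its power cannot be stated from the documents, which give neither the share of women tested nor the rates among them. Suppose 75% were tested, or 196 per arm. Pooled-variance power then depends on the assumed rates:

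| Assumed rates in the subset | Power at 196 per arm |
|---|---|
| 9.9% vs 18.4%, unchanged | about 68% |
| 4 points lower in each arm (5.9% vs 14.4%) | about 80% |
| 6 points lower in each arm (3.9% vs 12.4%) | about 87% |
| Both rates 20% lower (7.9% vs 14.7%) | about 57% |

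This range describes an added analysis, not a loss in the planned one. If the subset were defined by the embryo transferred, there would be a further difficulty. Transfer comes after randomisation, and section 4.5 cancels HRT cycles whose endometrium stays too thin. Women without a transfer would drop out, possibly more in one arm than in the other.

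**The case for a change.** The strongest case for acting is that the sentence in section 3 is unhedged, is the only reason given for choosing this population, and has no criterion behind it. It is also the text a report would draw on to attribute a difference to endometrial preparation in chromosomally normal embryos. If ploidy is not recorded, that reading cannot be checked afterwards, and any later subset would be chosen after the event. Defining one term and recording one item would cost little.

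Much of this stands. The written criteria do not secure the claim, and the term in section 4.3 is undefined. A report should not present the losses as non-aneuploid unless the centre's testing supports it.

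What does not stand is the step from there to a change in the plan. No objective, endpoint or test depends on the sentence. The protocol does not say whether ploidy is already recorded, so a failure to record it is not shown. A supportive subset analysis is commonly left to the SAP, which is not at hand. If one is made, its basis should be testing status known before randomisation.

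**Conclusion.** No change to the plan follows. The mismatch between section 3 and sections 4.2 and 4.3 is real as a matter of wording, and it is minor.

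- **Validity:** unaffected. Randomisation balances any aneuploid losses between arms on average, and the stated aim concerns PGT patients as a group.
- **Sample size:** unaffected, provided the enrolled women resemble the centre's 2017 PGT population. The 522 reproduces exactly.
- **Interpretation:** the only exposure. It depends on laboratory practice that the documents do not describe, so its size cannot be given. The share of losses that are aneuploid cannot be derived from the protocol.

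This is a gap that the centre's staff can fill from knowing what their own testing covers. Clarifying the term, and softening the rationale if testing does not cover ploidy, would tidy the text without altering who is enrolled, how many, or what is tested.

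### The late-miscarriage definition in Protocol 3.2 carries an unbracketed 'not', so read literally it counts only retained losses, unlike the parallel definition in 3.1 (minor)

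*Protocol*

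**What the plan says.** Section 3.1 (primary outcome) defines miscarriage before 8 weeks as a spontaneous loss "in which the embryo(s) is/are nonviable and is/are (not) spontaneously absorbed or expelled from the uterus". Section 3.2 (secondary outcomes) defines miscarriage after 8 weeks as "a spontaneous loss of a clinical pregnancy after 8 weeks but before 22 completed weeks of gestational age" and then adds the condition "in which the embryo(s) or fetus(es) is/are nonviable and is/are not spontaneously absorbed or expelled from the uterus". Both definitions cite the same 2017 source.

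Two other outcomes in 3.2 bear on the point:

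- Clinical pregnancy: "Clinical pregnancy defined as a pregnancy diagnosed by ultrasonographic visualization of one or more gestational sacs", or by definitive clinical signs. Documented ectopic pregnancy is included.
- Ongoing pregnancy: "Ongoing pregnancy rate defined as the number of pregnancies after 20 weeks of gestation".

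Section 4.5 says that in the HRT group, after a positive test, "estrogen and progesterone supplementation will be continued until 8 weeks of gestation".

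**The concern.** The two miscarriage definitions are built as successive windows on one event, and a reader will set the two rates side by side. The tail of the 3.2 definition is joined by 'and', so grammatically it is a required condition: the nonviable embryo or fetus must not have been absorbed or expelled. A loss at, say, 12 weeks that was spontaneously expelled would fail that condition.

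If outcome staff followed the wording, the late rate would be understated and would rest on a different event rule from the early rate. Late miscarriage is also the only listed outcome that directly measures loss after 8 weeks, the point at which supplementation in the HRT group ends.

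**Working it through.** **Step 1. The two definitions compared.**

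| Element | 3.1, early | 3.2, late |
|---|---|---|
| Opening | spontaneous loss of a clinical pregnancy | the same |
| Window | before 8 weeks | after 8 weeks, before 22 completed weeks |
| Cited source | 2017 source | the same |
| Negation in the tail | '(not)', bracketed | 'not', unbracketed |
| Retained loss counts? | yes | yes |
| Expelled or absorbed loss counts? | yes | no, if read literally |

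Apart from the window and the added mention of a fetus, the only difference of substance is the brackets. They decide the last row.

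**Step 2. Internal consistency of 3.2.** The opening admits any spontaneous loss of a clinical pregnancy in the window. An expelled loss is plainly such a loss, yet the tail excludes it. The two halves of the sentence therefore disagree.

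**Step 3. Is it corrected elsewhere?** The late definition is not restated. Section 5.2 deals only with "early miscarriage rates (defined as miscarriage before 8 weeks of gestation"), and section 5.1 defines no outcome.

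**Step 4. Size of the undercount.** Let L be the true late-loss rate in an arm and r the share of those losses that are retained.

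- Rate under the literal wording = r × L
- Amount missed = (1 − r) × L

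The protocol gives neither L nor r. With r anywhere from 0 to 1, the literal rule could report anything from none to all of the late losses. The exclusion applies throughout the window, 22 − 8 = 14 weeks.

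**Step 5. Effect on the comparison.** With arms A (NC) and B (HRT), the literal difference is r_B × L_B − r_A × L_A. If r is the same in both arms, this is r × (L_B − L_A): the absolute difference shrinks, while the ratio L_B / L_A is preserved. Only a different r in each arm would distort the ratio, and nothing in the protocol indicates that.

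**Step 6. Effect on the sample size.** Section 5.2 uses early rates only: 9.9% (NC) against 18.4% (HRT), two-sided 5%, 80% power, 1:1 allocation. With the unpooled normal approximation:

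- Variance sum = 0.099 × 0.901 + 0.184 × 0.816 = 0.0892 + 0.1501 = 0.2393
- n per arm = (1.960 + 0.842)² × 0.2393 / 0.085² = 260.01, rounded up to 261
- Total = 2 × 261 = 522, as stated

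The pooled-variance version gives 263 per arm, and power at 261 per arm is 79.7%. No late-loss figure enters, so correcting 3.2 leaves 522 unchanged.

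**The case against.** The strongest reply is that the text resists the literal reading. The opening words of 3.2 point to all spontaneous losses, the inclusive form stands just above in 3.1, and the shared source suggests that brackets were dropped. Staff who read it that way would record late losses correctly and no harm would follow. This stands as to consequence and is why the point is minor. It does not remove the point, because the sentence in 3.2 is the operative definition of a named outcome.

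Three stronger readings are tempting, and the protocol supports none of them.

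- **A gap among the outcomes.** A reader might infer that a pregnancy expelled between 8 and 20 weeks vanishes, being neither a miscarriage nor ongoing, and might size the gap as 20 − 8 = 12 of the 14 weeks. That mostly restates the same defect. Such a pregnancy is rightly absent from ongoing pregnancy; the only error is its absence from late miscarriage. Nor do the 12 weeks measure anything useful, since the literal exclusion covers all 14. The case also stays visible as attrition from clinical to ongoing pregnancy, although mixed with ectopic pregnancies and early losses.
- **Bias between arms.** Because HRT supplementation stops at 8 weeks, a reader might infer that the wording favours one arm. The same rule applies to both arms, and nothing suggests that the retained share differs. The stop at 8 weeks shows why late losses are of interest, not that the comparison is biased.
- **A faulty window.** A reader might also want the 8-week boundary restated to the day. That is a separate clarification, with no consequence shown here.

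**Conclusion.** The inconsistency is real. As written, 3.2 counts only retained losses from 8 to 22 weeks, conflicts with its own opening, and puts late miscarriage on a different event rule from early miscarriage. It is probably a drafting slip. Confidence is high for the difference in wording. Any effect on results depends on staff applying the sentence literally, which the protocol does not settle.

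The damage is confined to one secondary outcome and cannot be sized from the protocol. The primary outcome, its test and the sample size of 522 do not depend on it. One assumption lies behind this: section 5.1 does not say which miscarriage window the logistic regression uses, and I take it to be the primary one. Severity: minor.

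**What to change.** In section 3.2, put the word 'not' in the tail of the late-miscarriage definition in brackets, as in 3.1. A clearer alternative is to reword the clause as 'whether or not' the pregnancy has been absorbed or expelled. Leave the window limits, the primary outcome, its test and the sample size as they are.

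The cost is one phrase in one secondary definition. If late outcomes have already been coded, check that expelled and absorbed losses were recorded as miscarriages.
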